7.5 Data Quality Assurance

Investigators receiving federal funding must adhere to the Code of Federal Regulations (CFR) to protect research participants and produce reliable study information. Sites participating in research sponsored by the NICHD need to have an internal quality assurance (QA) plan that will identify problems and correct errors in research study records.

7.6 Role of Data Management

The AC and MC will provide instructions concerning the recording of study data on the CRFs, submission of CRFs, and administration and transmission of ACASI data.

7.7 Study Site Monitoring and Record Availability

Site monitors from the MC and AC will visit participating study sites to review a selected portion of the individual participant records, including assent/consent forms, CRFs, and supporting source documentation to ensure the protection of study subjects, compliance with the protocol, and accuracy and completeness of records. Regulatory files, as required, will also be inspected to ensure that regulatory requirements are being followed.

The site investigator will make study documents (e.g., assent/consent forms, case report forms) readily available for inspection by the local IRB, the central IRB, the site monitors, the NICHD, the Office for Human Research Protections (OHRP), or the sponsor's designee for confirmation of the study data.

8.0 PARTICIPANT MANAGEMENT

8.1 Tracking Participants / Follow-up

Study staff will verify participant contact information at baseline and update this information if needed at time of follow up.

Study staff will contact participants prior to their target date to complete follow-up study procedures. Study staff will use both a preferred and, if necessary for YYA who are difficult to reach, backup method of contact as indicated at baseline (e.g. mail, alternate phone numbers, e-mail, text message, social media contact information), to contact participants to complete follow up study procedures. Additional reminders will be provided on/after the target date as needed to ensure completion of study visit procedures. Participants will be asked whether or not messages can be left for each of the phone numbers that they provide. They will be informed that messages will not contain any information regarding the nature of the project.

8.2 Compensation

The method and amount of compensation will be determined separately by each site, listed in the site's informed consent/assent form, and approved by the central IRB (the UNC-CH IRB). RCT participants will be compensated at each of their appointments at the SRV, including the enrollment/baseline visit and each of the 3-, 6-, and 9-month assessment points.

8.3 Intervening on "Social Harms"

We identified the following 3 items as possible risks to subjects for the overall study period and described how we plan on addressing those risks:

1. Protecting against others finding out about their gender identity during focus groups. Participants will be alerted to this given that the focus groups are in person. The description of the purpose of the study will clearly state that the study is designed to promote face-to-face discussion with other trans YYA, and we will recommend that persons who are highly uncomfortable with such exchanges may be better served by not enrolling in the study. Once enrolled, we also minimize this risk of identification to participants by asking participants to come up with a pseudonym that do not contain personally identifying information. Additionally, we will establish "group rules" that include requesting that no information about the identity of participants or what is said in the focus group is shared outside of the focus group. Although we cannot guarantee their anonymity, we will take appropriate safeguards to minimize this risk.
2. Protecting against discomfort in answering personal questions during the focus group discussions. This risk is similar to #1 above, and we will use comparable safeguards to protect against it. Thus, we intend to fully inform participants of the purpose and nature of the study prior to their participation. Participants are informed that they are free not to answer questions, and they may stop participation at any time. Since a "decline to answer" option is provided to the survey completed just before the focus group, there is a constant reminder of their participant rights throughout the study. Thus, we believe the risk to participants is minimal and we have adequately anticipated and set into place protocols to address potential risks that may arise.
3. Protecting against concerns about the security of their data during focus groups and RCT. Well-established security processes will be followed, that include the following:
 - Participants' identifying information is housed in a separate cloud-based password-protected study management platform, SMART, which is separate from survey data and other collected outcome data. Only authorized study staff will be granted access

to the platform through requests initially made to the Analytic Core at Emory University, or subsequently through the designated study coordinator. SMART regulates staff permissions to view participant information based on assigned user roles, which also stratifies participant data by site/location, such that staff from other sites will not be able to view participant data except from their site/location. Study staff will not be able to download participant data from the cloud-based platform. Only designated analysts at the Analytic Core at Emory University will have access to data downloads from SMART for reporting purposes.

- At the end of the study, the identifying information (participants' names and contact information) is destroyed. The original data records will be archived for a minimum of 3 years following the conclusion of the study or longer if institutional requirements dictate, and three copies of the de-identified dataset will be maintained (a working one and two archived at different sites).
- All project staff will be required to complete the NIH online training in research ethics. Further training and supervision will focus research staff on confidentiality concerns both during and after the study. The project coordinator in conjunction with the Protocol Chairs are responsible for ensuring that all research staff involved in this study document their NIH training.

There are two risks associated with receiving the WebApp:

1. Protecting against going to the site by mistake. We have a secure site ([https:](https://)) with an introductory page clearly specifying the nature of the study. Sensitive survey or intervention content is protected behind screening questions and a username/password, and therefore in the opening study webpage, we could not think of anything that would be deemed offensive by any persons or those who might be vulnerable. In this way, we have minimized the risk to a level that is negligible.
2. Protecting against hostile interactions and inaccurate information from one participant to another. Participants will be informed during the onboarding process of the "group rules" regarding interactions with one another (e.g., "Honesty is important; however, hostile or abusive language will not be tolerated and may be grounds for immediate removal from the study"). These "rules" will also be available with a link on all intervention web pages for review by participants at any time. The project coordinator will manually review an automated compilation of posts participants make on a daily basis to flag hostile interactions and inaccurate information. Hostile interactions between participants will be handled by, first, reminding the participants in the interaction of the "group rules" regarding appropriate interactions. If the hostility continues, the offending participants will be given a warning that the continued hostility will result in withdrawal from the study if it continues. On the third offense, the participant may be withdrawn from the study after discussion of the offense. Text containing hostile exchanges will be removed from the study website and unavailable to view. In cases in which inaccurate information is found, project staff be guided by experts on the team to post a comment that provides accurate information on the topic. In extreme cases, the Protocol Chairs or SRV Site PIs may decide to withdraw a participant before the third offense. We will ensure all clinic sites have a clear clinical protocol to address major issues that may come up at study visits or in online interactions. The major issues addressed in the protocol will be suicidal ideation, homicidality or violent ideation, emotional and cognitive disregulation, violent/aggressive or disruptive behavior, and intoxication. If research staff see concerning comments or messages online from participants regarding self-harm or harm of others, they will contact study site staff and take immediate precautions.

All sites have specific policies governing the treatment of human subjects. These policies specify that medical and psychological assistance will be available in the immediate environment in the event a participant should experience any adverse reactions resulting from study procedures.

While participants will be informed that they may refuse to answer any question at any time, responses or reactions to certain questions may indicate distress on the part of the participants. If at any time during the study, a participant divulges that he or she is at risk for harm, including but not limited to being abused or experiencing violence, if harm is suspected or likely, or if the participant states he or she is suicidal/homicidal, measures will be taken to ensure his or her safety. Reporting will be done as appropriate to the situation and the legal statutes, including reporting to child protection agencies or other appropriate agencies, and referrals will be provided to appropriate support, counseling, or treatment resources.

See section 11.3.1 for more information on potential social harm-related risks.

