8.4 Criteria for Premature Study Discontinuation

The Protocol Chairs and SRV Site PIs have the authority to withdraw any participant at any time if in their opinion it would be in the best interest of the participant. The participant will be informed of this withdrawal and explained the rationale. Withdrawal will be documented in the study tracking system. If a participant is withdrawn due to seroconversion, they will be offered referrals and linkages as necessary, and may be referred to an ATN study for HIV+ participants.

Participants will be prematurely discontinued from the study if any of the following occurs:

- The participant withdraws consent/assent
- The participant is unwilling or unable to comply with study procedures
- The participant fails to return or confirm HIV negative test results with research staff within 90 days of their enrollment visit
- The participant returns a HIV positive test result at the 3- or 6-month follow-up time point.
- The participant seroconverts
- The Protocol Chairs or Site PIs believe that ongoing participation may cause harm to the participant or study staff
- The Protocol Chairs or Site PI believe that ongoing participant may impact the integrity of the study dataThe study is cancelled by the NIH (or iTech, or other administrative entity);
- The study is cancelled for other administrative reasons;
- Death of the participant

Participants may end their participation in the study at any time. No further data collection will occur from the date the decision is made to permanently discontinue the subject from the study. Participants who experience distress during the study while in the SRV clinic will be offered counseling on site. Participants who experience distress during the study and do not come to the SRV clinic for a visit will be provided a list of community referrals via phone or e-mail. Any unexpected adverse events that meet the unanticipated problem (UP) reporting criteria will be immediately reported to the UNC-CH IRB and the respective sites' IRBs if applicable. The *Study Stop CRF* will be completed at this time.

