11.3 Risks and Benefits

11.3.1 Risks

Risks to participants in this research study may include:

Potential participants or participants enrolled in the study may have concerns about others finding out about their gender identity or other personal behavior (e.g., sexual behavior or substance use). We anticipate that the likelihood of this occurring is high for those randomized into the App+Step arm given that a major feature of the WebApp is for participants to network with one another and that eligibility for enrollment in the study requires participants to be a trans youth or young adult. We anticipate that the likelihood of this occurring is high during the focus groups as well, since they will be meeting in-person with other trans YYA for the focus groups. Subjects will be informed of the inclusion criteria and general questions that will be asked during focus groups during the recruitment period. Since subjects will be recruited directly within SRVs, they will have the opportunity to discuss with staff whether they feel comfortable being a part of such discussions. Clear consent procedures will also give opportunities for subjects to withdraw if they no longer feel comfortable participating in focus group discussions. For those in the RCT, subjects will be informed during the consent process of the basic features of the WebApp intervention and those who are not comfortable interacting with other trans YYA will be encouraged to not participate in the study.

To minimize the risk of participants feeling uncomfortable about answering personal questions, we will provide an option for online methods for screening. For assessments, we will use ACASI methods for the study's surveys. In ACASI, participants read and hear aloud survey questions on a computer and use a combination of mouse click and keyboard/touchscreen entry to input the answers themselves. Study staff may be available to assist participants with questions or technical difficulties on the online screener of the ACASI. Participants will also be able to refuse to answer any question that makes them uncomfortable.

Participants in the focus groups will be told of "group rules" at the beginning of the focus group, which includes asking them to not share the identities of attendees or content shared during the focus group.

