The measurements that are involved in this study require venipuncture to collect blood samples for syphilis testing. Syphilis is tested by serum RPR performed by a trained and certified phlebotomist. This procedure may cause local discomfort, bleeding, or bruising; rarely small clot or infection can occur at the blood draw site. This measurement should not be considered greater than minimal risk in and of itself given its routine use in general health care delivery.

Urine samples will be provided to test for gonorrhea, Chlamydia, and current drug use and will be collected under monitored conditions (i.e., using an FDA approved temperature strip to verify the specimen integrity). Pharyngeal swabs are taken from the back of the throat to test for gonorrhea and Chlamydia and participants self-administer rectal swabs for gonorrhea and Chlamydia.

Trained and certified research assistants will perform dried blood spot extraction. The procedure will only require a finger prick to extract a small amount of blood, and therefore the risk of infection or bruising is small. If needed, clinical staff will be on site to assist with any medical problems that may arise from this procedure.

Participants randomized into the App+Step arm may receive hostile communications or incorrect information from other participants during the course of the WebApp component. It is possible that some participants may respond aggressively or with hostility to other participants. Likewise, although well-intended, participants may provide inaccurate information about adherence or its risk factors to other participants by interactions through the website message boards/social networking wall. The WebApp intervention will include a clear section on Community Guidelines and will be monitored daily by research staff. Users have the option to “flag” objectionable content. We have protocols in place for addressing hostile interaction in the site up to and including termination of participation in the study.

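### The WebApp hostility rule ends follow-up as well as app use, so App+Step alone is exposed to an outcome loss of unknown size and direction

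*Combined protocol and SAP*

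**What the plan says.** Section 8.3 introduces the rule under a list that opens "There are two risks associated with receiving the WebApp". Hostile exchanges between participants lead first to a reminder, then to a warning. After that, "On the third offense, the participant may be withdrawn from the study after discussion of the offense". The sequence can be shortened: "In extreme cases, the Protocol Chairs or SRV Site PIs may decide to withdraw a participant before the third offense". Section 11.3.1 states the same sanction: "We have protocols in place for addressing hostile interaction in the site up to and including termination of participation in the study". Neither section has a step that removes only posting rights or app access.

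Section 8.4 gives the consequence for the data: "No further data collection will occur from the date the decision is made to permanently discontinue the subject from the study". It also lets the Protocol Chairs and site PIs withdraw participants of any arm on best-interest, harm or data-integrity grounds, and it requires a Study Stop CRF.

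Section 11.3.1 shows which arm is affected. It says that "a major feature of the WebApp is for participants to network with one another", and that "Participants randomized into the App+Step arm may receive hostile communications or incorrect information from other participants during the course of the WebApp component". No peer-to-peer posting is described for Text+Step or Info.

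Sections 10.3.2 and 10.4 assign missing RCT data to LTMLE, with a dropout regression on baseline and time-varying covariates. The covariates are not listed.

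**The concern.** Hypotheses 1a and 1b in Section 2.0 compare each active arm with Info, and Section 1.1 puts the primary endpoint at month 6. A removal triggered by behaviour after randomisation, which can occur in one arm only, is the kind of loss that can undo the balance randomisation provides. If those removed differ in sexual risk or PrEP use from those who stay, the App+Step results describe a selected group while Info has no matching selection. The person deciding on removal also necessarily knows the arm.

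The loss reaches further than the hazard it answers. The hazard arises from posting. Section 5.3.3 ends access to the assigned intervention for everyone after month 6, so month-9 outcomes are in any case collected without the app. Yet a participant withdrawn in month 2 loses months 3, 6 and 9. That participant also misses the month-3 assessment that decides eligibility for the eCoaching re-randomisation, so Secondary Aim 3 loses the case too.

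**Working it through.** **1. The textual chain.**
- What is the participant withdrawn from? The study (Sections 8.3 and 11.3.1), not the app.
- What follows? Data collection stops (Section 8.4).
- Which arm can this trigger reach? Only App+Step (the WebApp risk list in 8.3; 11.3.1). The general powers in 8.4 cover all arms, but this rule and its daily review of posts have no counterpart in Text+Step or Info.

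**2. The plan's own figure.** Section 10.2.2 claims more than 80% power for an average decrease of 1.5 risky encounters, with dropout of 5-15%. This cannot be reproduced: the SD, alpha, baseline rate and simulation settings are not given. As a scale check only, assume a two-sided 0.05 test of two means with 83 per arm. The SD giving exactly 80% power is

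SD = 1.5 / [(1.960 + 0.842) × √(2/83)] = 3.45,

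or 3.36 with 5% dropout and 3.18 with 15%. This neither confirms nor refutes the claim. At SD 3.45, removing 1, 2, 4 or 8 App+Step participants lowers power from about 80.0% to 79.7%, 79.5%, 79.0% or 77.9%. Lost precision is therefore a minor matter; the issue is selection.

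**3. Shift in an unadjusted App+Step mean.** Let w = k/83 be the share removed and D the mean outcome of those removed minus that of those retained. Then

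full-arm mean − retained mean = w × D.

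The 83 is from Section 3.2 and the 1.5 from Section 10.2.2. **k and D are assumptions; the documents give neither.** Each cell shows the shift in encounters and, in brackets, its share of 1.5.

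| Removed (k) | w | D = 1.5 | D = 3 | D = 5 | D = 10 |
|---|---|---|---|---|---|
| 0 | 0 | 0 | 0 | 0 | 0 |
| 1 | 1.2% | 0.02 (1%) | 0.04 (2%) | 0.06 (4%) | 0.12 (8%) |
| 2 | 2.4% | 0.04 (2%) | 0.07 (5%) | 0.12 (8%) | 0.24 (16%) |
| 4 | 4.8% | 0.07 (5%) | 0.14 (10%) | 0.24 (16%) | 0.48 (32%) |
| 5 | 6.0% | 0.09 (6%) | 0.18 (12%) | 0.30 (20%) | 0.60 (40%) |

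Example: (5/83) × 5 = 0.30, and 0.30/1.5 = 20%. For the shift to reach 10% of the effect (0.15 encounters), D must be 0.15 × 83/k: 12.5 for one removal, 6.2 for two, 3.1 for four and 2.5 for five. A negative D reverses the sign.

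**4. What the planned analysis adds.** The table describes a completers' mean, not the LTMLE estimate. LTMLE removes the part of the difference that its covariates explain. The plan does not say whether these removals count as dropout, or whether app conduct or reason for withdrawal enters the dropout model. It names no sensitivity analysis for missing data. The remaining bias therefore cannot be calculated from the documents.

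**5. With follow-up separated from app removal.** For each removed participant who accepts the invitation to assessments, the contribution to w is zero, and so is the shift.

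**The case against.** The strongest reply is that the event may be rare and that the analysis is built for it. Removal is discretionary and normally follows a reminder and a warning. Posts are reviewed daily and hostile text is taken down. With one or two removals and a difference of 5 encounters or less, the unadjusted shift is at most 0.12 encounters. LTMLE is specified because missingness may be informative. Everyone removed has baseline data, and those removed after month 3 can have month-3 data as well. The abstract also provides for process data on participant activity, so app conduct could be used to model dropout within App+Step; no matching variable is needed in the other arms. All of this stands, and it limits the size of the point.

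A reader might go further and infer that the App+Step comparison is biased, that the arm will look better because it expels its worst cases, or that the dropout model cannot repair the loss. The documents support none of these. Bias needs removals to occur, an outcome difference, and a failure of the covariates to explain it. Nothing in the documents links hostile posting to higher sexual risk, so the direction is open. The fair statement about LTMLE is that it is not shown to deal with these cases, not that it cannot.

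The reply does not answer the structural point. The loss is confined to one arm, the protocol itself creates it, and data never collected cannot be recovered by analysis.

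**Conclusion.** The point holds as an avoidable exposure, not as a demonstrated bias. The protocol makes the end of follow-up the sanction for conduct that can occur only in App+Step, and so allows arm-specific, possibly outcome-related loss in that arm's primary comparison with Info. Size and direction are unknown. On assumed inputs of 1 to 5 removals out of 83 and a 5-encounter difference, an unadjusted mean shifts by 0.06 to 0.30 encounters, or 4% to 20% of the 1.5-encounter effect. With no removals the shift is zero, and the planned LTMLE may make it smaller. The case for acting rests on the low cost of avoiding the loss rather than on a large expected effect.

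**What to change.** In Sections 8.3 and 11.3.1, distinguish loss of the WebApp's social features or access from withdrawal from follow-up. State that a participant removed for hostile posting:
- remains in App+Step as randomised; and
- where willing, and where no existing Section 8.4 criterion applies, is still invited to the scheduled month-3, 6 and 9 assessments, online if needed. The abstract already allows online visits and an online ACASI.

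Record the reason and date of removal, for example by extending the Study Stop CRF or the tracking record that Section 8.4 already requires. In Section 10.3.2, say whether app conduct and reason for withdrawal enter the dropout model.

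Leave the offense steps and all Section 8.4 discontinuation grounds as they are; no view is taken here on how hostile conduct should be managed. The cost is a wording change in the protocol and onboarding text, one or two recorded fields, and continued staff contact with a few disruptive participants.
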